6.2 Study Dates

Informed Consent Date

The date on which the subject signs the study informed consent form.

Enrollment Date

The date on which the subject is enrolled in the study.

First IP Dose Date

First IP dose date is the date on which a subject is administered the first dose of IP in study 20130255, which may be the same or after the enrollment date. Subjects who are enrolled should be dosed at least on day 1. If a subject is enrolled but not dosed, first IP dose date is set to first available dose date.

Last IP Dose Date

End of IP dose date for each subject is defined as the latest date IP is administered.

End of IP Admin Date

End of IP admin date for each subject is defined as the date the decision was made to end IP as recorded on the end of IP CRF page.

Subject-level End of Study (EOS) Date

End of study (EOS) date for each subject is defined as the last date on which the subject participated in the study. The date will be recorded on the end of study eCRF page.

Study Completion Date

The study completion date is the EOS date of the last subject in the study.

6.3 Study Points of Reference

Baseline

There are two baselines for this study: one is based on the 20120295 parent study baseline and other is based on the 20130255 study baseline.

The 20120295 parent study baseline is the baseline defined in the 20120295 parent study. For monthly efficacy endpoints, the baseline is derived using the parent study data from the first day subject used eDiary in baseline phase at week-4 study visit through the day prior to study day 1 of the parent study 20120295. For safety endpoints, the baseline is the last non-missing assessment for the endpoint of interest taken before day 1 IP dose in the parent study 20120295.

In addition, for monthly rate or monthly average of migraine and non-migraine headache related efficacy endpoints, 20130255 study baseline is also used and derived using the parent study 20120295 month 3 data (ie, week 8 through week 12 data). For safety endpoints, 20130255 study baseline is the last non-missing measurement (including measurements taken from 20120295) for the endpoint of interest taken before day 1 IP dose in the study 20130255. For C-SSRS, all individual items from the parent

study 20120295 week 12 visit will be used as 20130255 study baseline if available, **otherwise baseline as defined in the parent study will be used.**

Study Day 1

Study day 1 is defined as the first IP dose date in the study 20130255. For subjects who are enrolled but not dosed after enrollment, the study day 1 is defined as the date of enrollment.

Study Day

Study day is defined as the number of days from study day 1.

Before study day 1:

$$\text{Study day} = (\text{date of Interest} - \text{date of study day 1})$$

On or after study day 1:

$$\text{Study day} = (\text{date of Interest} - \text{date of study day 1}) + 1$$

The day prior to study day 1 is -1.

6.4 Study Time Intervals

Monthly Interval for Efficacy Endpoints

Monthly efficacy measurements will be calculated based on the subject's monthly IP dosing schedule defined below using eDiary data collected from day 1 up to week 48 (end of eDiary use). Any eDiary data occurring after EOS date will not be included in the analysis.

Week	Interval Based on Dose Dates for OLE Phase	
	Start date	End date
4	Day 1 dose date	Week 4 dose date-1; study day 28 if week 4 dose is not received (either missed or IP discontinued prior to week 4)
8	Week 4 dose date; study day 29 if week 4 dose is not received (either missed or IP discontinued prior to week 4)	Week 8 dose date-1; study day 56 if week 8 dose is not received (either missed or IP discontinued prior to week 8)
12	Week 8 dose date; study day 57 if week 8 dose is not received (either missed or IP discontinued prior to week 8)	Week 12 IP dose date-1; study day 84 if week 12 dose is not received (either missed or IP discontinued prior to week 12)
16	Week 12 dose date; study day 85 if week 12 dose is not received (either missed or IP discontinued prior to week 12)	Week 16 IP dose date-1; study day 112 if week 16 dose is not received (either missed or IP discontinued prior to week 16)
20	Week 16 dose date; study day 113 if week 16 dose is not received (either missed or IP discontinued prior to week 16)	Week 20 IP dose date-1; study day 140 if week 20 dose is not received (either missed or IP discontinued prior to week 20)
24	Week 20 dose date; study day 141 if week 20 dose is not received (either missed or IP discontinued prior to week 20)	Week 24 IP dose date-1; study day 168 if week 24 dose is not received (either missed or IP discontinued prior to week 24)
28	Week 24 dose date; study day 169 if week 24 dose is not received (either missed or IP discontinued prior to week 24)	Week 28 IP dose date-1; study day 196 if week 28 dose is not received (either missed or IP discontinued prior to week 28)
32	Week 28 dose date; study day 197 if week 28 dose is not received (either missed or IP discontinued prior to week 28)	Week 32 IP dose date-1; study day 224 if week 32 dose is not received (either missed or IP discontinued prior to week 32)
36	Week 32 dose date; study day 225 if week 32 dose is not received (either missed or IP discontinued prior to week 32)	Week 36 IP dose date-1; study day 252 if week 36 dose is not received (either missed or IP discontinued prior to week 36)
40	Week 36 dose date; study day 253 if week 36 dose is not received (either missed or IP discontinued prior to week 36)	Week 40 IP dose date-1; study day 280 if week 40 dose is not received (either missed or IP discontinued prior to week 40)
44	Week 40 dose date; study day 281 if week 40 dose is not received (either missed or IP discontinued prior to week 40)	Week 44 IP dose date-1; study day 308 if week 44 dose is not received (either missed or IP discontinued prior to week 44)
48	Week 44 dose date; study day 309 if week 44 dose is not received (either missed or IP discontinued prior to week 44)	Week 48 IP dose date-1; study day 336 if week 48 dose is not received (either missed or IP discontinued prior to week 48)
52	Week 48 dose date; study day 337 if week 48 dose is not received (either missed or IP discontinued prior to week 48)	Study day 364

Note: for the intervals in month 6, 10, and 13 all available data before the next planned IP dose or visit should be used for calculation. Also refer to the definition of Monthly Migraine Days in [Section 6.1.2](#).

Study Visit

Since the actual visit for a subject may not exactly coincide with his/her targeted visit date, the actual visit date is mapped to the study visit as follows (visit windows below only apply to visits other than safety follow-up visit):

Study Phase	Study Visit	Target Day	Study Day
Open-label Treatment Phase	Day 1	1	1
	Week 4	29	2-43
n = 2 to 13	Week 4n	28n+1	28n-12 to 28n+15
	Week 8	57	44-71
	Week 12	85	72-99
	Week 16	113	100-127
	Week 20	141	128-155
	Week 24	169	156-183
	Week 28	197	184-211
	Week 32	225	212-239
	Week 36	253	240-267
	Week 40	281	268-295
	Week 44	309	296-323
	Week 48	337	324-351
	Week 52	365	352-379
	Safety Follow-up	The nominal visit from RAVE	

Note: If more than one visit (including the unscheduled visits, ie, CPEVENT='UNSCHED') fall within the same defined window, **scheduled visit will be used regardless of the distance from the target day. Unscheduled visit will only be used when there is no scheduled visit in the defined window.** The closest visit to the target day **among the same type of visit (scheduled vs. unscheduled)** will be considered for analysis. If two assessment dates are equidistant from the target date, the latter visit will be considered for analysis.

Above study visit table will be used for lab, vital signs, C-SSRS and PROs collected during office visit.

For adverse event, analysis windows will be set up based on study phase:

Study Phase	Start Time Point	End Time Point
Screening Phase for SAE only	Informed consent date	One study day prior to the first IP dose
Open-label Treatment Phase	Study Day 1 after the 1 st IP Dose	Min(EOS date, last IP dose date + 112 days)

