6.1.2 Efficacy Endpoints

eDiary Day

Day in which a subject uses the eDiary.

Migraine Day

A migraine day is any calendar day in which the subject experiences a qualified migraine headache. A qualified migraine headache is defined either as a migraine with or without aura as outlined below:

1. A migraine without aura is defined as a headache lasting continuously for ≥ 4 hours, and meeting criteria a and/or b:
 - a) ≥ 2 of the following pain features:
 - Unilateral
 - Throbbing
 - Moderate to severe
 - Exacerbated with exercise/physical activity
 - b) ≥ 1 of the associated symptoms:
 - Nausea and/or vomiting
 - Photophobia and phonophobia

OR

2. A migraine with aura and meeting criteria c and d:
 - c) The occurrence of ≥ 1 of the following fully reversible aura symptoms:
 - Visual
 - Sensory
 - Speech and/or language
 - Retinal
 - Brainstem
 - d) Aura is accompanied, or followed within 60 minutes, by headache lasting continuously for ≥ 4 continuous hours (see [Appendix C](#)).

If the subject took a triptan or ergot-derivative during aura or to treat headache on a calendar day, then it will be counted as a migraine day regardless of the duration and pain features or associated symptoms.

Monthly Migraine Days

Monthly migraine days is the number of migraine days **between each monthly IP dose normalized to 28 day equivalents**, relative to study day 1 in the first 3 months, between the month 5 and 6 visit, between the month 9 and 10 visit and **between the month 12 and 13 visit**. Hereafter, the corresponding visits for these intervals will be reported/presented as/referred to month 1, month 2, month 3, month 6, month 10 and

month 13 visit, respectively. All available eDiary data for the visits will be used and prorated to 28-day equivalents.

Qualified Headache

A migraine or non-migraine headache which lasts ≥ 4 continuous hours, or a headache of any duration for which acute medication was administered for treatment of headache.

In particular, a qualified headache is:

- a qualified migraine headache (including an aura-only event that is treated with acute migraine-specific medication), or
- a qualified non-migraine headache, which is a headache that lasts continuously for ≥ 4 hours and is not a qualified migraine headache, or
- a headache of any duration for which acute medication is administered.

Headache Day

Any calendar day in which the subject experiences a qualified migraine or non-migraine headache.

Monthly Headache Days

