Number of days on which medications are used for acute treatment of headache **between each monthly IP dose and normalized to 28 day equivalent** relative to study day 1 in the first 3 months, or between the month 5 and 6 visit, or between the month 9 and 10 visit, or **between the month 12 and 13 visit**. **Days without eDiary data are handled by proration according to [Section 9.3](#)**.

Monthly Acute Migraine-specific Medication Use in Days

Number of days on which migraine-specific medications are used **between each monthly IP dose and normalized to 28 day equivalent** relative to study day 1 in the first 3 months, or between the month 5 and 6 visit, or between the month 9 and 10 visit, or **between the month 12 and 13 visit**. **Days without eDiary data are handled by proration according to [Section 9.3](#)**.

Monthly Average Severity of Migraine Pain

Severity of migraine pain is graded as 1=mild, 2=moderate or 3=severe and was rated as its worst or peak intensity per migraine headache. Monthly average severity of migraine pain was defined as the sum of the severity of each observed qualified

migraine day **between each monthly IP dose and normalized to 28 day equivalent** relative to study day 1 in the first 3 months, or between the month 5 and 6 visit, or between the month 9 and 10 visit, **or between the month 12 and 13 visit** divided by the total number of observed qualified migraine days (**as one record in eDiary with start and end time**) in the corresponding interval. **If less than 14 days of eDiary in each interval is recorded, then the monthly average severity of migraine pain will be set as missing.**

Monthly Average Severity of Migraine Symptoms

Migraine Symptoms include nausea, vomiting, photophobia and phonophobia. Severity of these symptoms is graded as 1=mild, 2=moderate or 3=severe and 0 if not reported for qualified migraine headache. Monthly average severity of each migraine symptom was defined as the sum of the severity of corresponding migraine symptom **between each monthly IP dose and normalized to 28 day equivalent** relative to study day 1 in the first 3 months, or between the month 5 and 6 visit, or between the month 9 and 10 visit, **or between the month 12 and 13 visit** divided by the total number of observed qualified migraine days in the corresponding interval. **If less than 14 days of eDiary in each interval is recorded, then the monthly average severity of migraine symptom will be set as missing.**

CCI

CCI

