6.5 Subject Disposition

Enrolled

Individuals are considered enrolled if they have non-missing enrollment date. Enrolled individuals are referred to as “subjects”.

Completing the Open-label Treatment Phase

Subjects are defined as completing the open-label treatment phase if they complete the week 52 assessment, which means the subjects have completed the end of IP form and have eDiary data for the month 13.

Completing Study

Subjects are defined as completing the study if they complete the whole 64 weeks of study evaluation. It will be derived from the end of study CRF page with “completed” as the primary reason for ending study.

Exposed to Investigational Product

Subjects are defined as exposed if they receive at least one dose of investigational product in study 20130255.

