6.6 Arithmetic Calculations

Exposure

For calculations of exposure, dose date refers to receiving dose > 0, but can include partial doses. The non-AE safety treatment group assignments will be based on the durations of IP exposure to AMG 334 70 mg and 140 mg as presented below (see also [Appendix C](#)).

Duration of IP Exposure for Subjects Receiving Only 70 mg or 140 mg

Duration = minimum (last dose date + 27, EOS date) – first dose date + 1.

Duration of IP Exposure for Subjects Receiving Both 70 mg and 140 mg

70 mg duration = minimum (first 140 mg dose date - 1, last 70 mg dose date + 27, EOS date) – first 70mg dose date + 1.

140 mg duration = minimum (last 140 mg dose date + 27, EOS date, date of data cut off) – first 140 mg dose date + 1.

Change from Baseline in Monthly Efficacy Measurement

The change from baseline in monthly efficacy measurement is the monthly efficacy measurement in **between consecutive exposures to IP** prior to the given time point minus the baseline monthly efficacy measurement (see Interval Based on Dose Dates for OLE Phase table presented in [Section 6.4](#)). For example, the change from baseline in monthly migraine days at week 12 will be calculated as:

(Monthly migraine days between week 12 interval start date and week 12 interval end date) – Baseline monthly migraine days

If the baseline or post-baseline value is missing, then the change from baseline is set to be missing.

Following efficacy endpoints will be calculated as above:

Secondary endpoints

- change from baseline in monthly migraine days
- change from baseline in monthly acute migraine-specific medication treatment in days
- **change from baseline in cumulative monthly headache hours**

Exploratory endpoints

- change from baseline in monthly migraine attacks
- change from baseline in monthly headache (migraine and non-migraine headache) days
- change from baseline in monthly moderate and severe headache (migraine and non-migraine headache) days
- change from baseline in monthly average severity of migraine pain
- change from baseline in monthly average severity of migraine related symptoms (nausea, vomiting, phonophobia, photophobia) for qualified migraine headaches
- **Change from baseline in migraine-specific quality of life, as measured by the MSQ, version 2.1**
- **Change from baseline in migraine-related disability, as measured by the MIDAS**

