9.3 Handling of Missing and Incomplete Data

Subjects may miss specific data points for a variety of causes. In general, data could be missing due to a subject's early withdrawal from study, a missed visit, or inability to evaluate an endpoint at a particular point in time. For this study, most of the efficacy endpoint will be collected via eDiary and subjects could miss entering several days of data **in between exposures to IP**. The general procedures outlined below describe what will be done when a data point is missing.

Missing eDiary data in the calculation of monthly measurements about subjects' migraine and non-migraine headaches will be handled **using method below**. Unless otherwise specified, all the final analysis and sensitivity analysis will use monthly measurements calculated as follows:

1. **For monthly intervals with ≥ 14 days of eDiary days (days subjects use eDiary and including retrospective eDiary days) in each interval:**
 - a) Monthly frequency measurements (including migraine days, headache days, migraine attacks, cumulative hours of migraine headaches, cumulative hours of migraine headaches with severe pain, acute medication use, etc.) will be

prorated to 28-day equivalents. **Prorated result does not need to be rounded.**

- b) Monthly average severity of migraine pain, migraine related symptoms, **physical impairment scores and impact on everyday activities scores as measured by MPFID** and monthly average scale of migraine interference with daily activity will be calculated as the average of observed scores.
2. **For monthly intervals with < 14 days of eDiary use (including retrospective eDiary days)**, all monthly measurement will be set as missing and will be handled as described in [Section 9.3.2](#)

An information day is a calendar day which is either an eDiary day or headache day and will be used toward headache day proration. The eDiary days will be used toward migraine day proration and medication use day proration.

Missing PROs (MSQ, MIDAS) collected at office visit at certain assessment will not be imputed.

Missing safety endpoints will not be imputed. **Missing day portion of AE start time will be imputed based on [Section 9.3.1](#).**

Missing pharmacokinetic and antibody data will not be imputed.

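### SAP 6.4 stops eDiary input at week 48, which is where the month-13 diary interval begins; read literally, month 13 is lost for all four secondary endpoints

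*SAP*

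**What the plan says.** The first sentence of SAP 6.4 (Monthly Interval for Efficacy Endpoints) sets the data that feed the monthly measures: they are calculated "using eDiary data collected from day 1 up to week 48 (end of eDiary use".

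Other passages treat week 48 as the start of a diary interval that still has to be analysed:

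- **SAP 6.4, interval table, week 52 row:** the interval starts at "Week 48 dose date; study day 337 if week 48 dose is not received" and ends at study day 364.
- **SAP 6.4, note under the table:** "for the intervals in month 6, 10, and 13 all available data before the next planned IP dose or visit should be used".
- **SAP 6.1.2:** monthly migraine days are defined for a last interval "between the month 12 and 13 visit", reported as month 13. The other monthly eDiary counts, including migraine-specific medication days and cumulative headache hours, use the same interval.
- **SAP 6.5:** a subject completes the open-label phase by completing week 52, "which means the subjects have completed the end of IP form and have eDiary data for the month 13".
- **SAP 6.6:** change from baseline is calculated from the interval table ("see Interval Based on Dose Dates for OLE Phase table presented in" Section 6.4).
- **Protocol synopsis and 7.2.1.10:** the diary is completed daily between the month 12 and month 13 visits. Table 1 equates week 48 with month 12 and week 52 with month 13, and its row for bringing the eDiary to site is marked at week 52 and not at week 48.

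**The concern.** The sentence states which data enter the calculation, so a programmer could reasonably apply it as a filter before the interval table is used. That filter would remove nearly all of the month-13 interval. SAP 9.3 says that for an interval with fewer than 14 eDiary days "all monthly measurement will be set as missing", and SAP 9.3.3 bases the primary efficacy analysis on observed data without imputation. Nothing later in the plan would restore the time point.

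At stake is the month-13 result for all four secondary endpoints: change in monthly migraine days, the 50% responder endpoint, change in migraine-specific medication days, and change in cumulative headache hours. The last eDiary efficacy result would then be month 10, in an extension whose secondary objective is long-term efficacy. The label in the sentence also conflicts with SAP 6.5: if diary use ended at week 48, no subject could meet the definition of completing the open-label phase.

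**Working it through.** **Inputs**

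- Interval limits: SAP 6.4 table.
- Visit window of ±4 days: protocol 7.1. Assumption: visits fall within it.
- Target days 28n + 1: SAP 6.4 study visit table.
- Home dose one day after the week 48 visit, for home-use substudy subjects who start at week 40: protocol 7.2.1.16.
- Minimum of 14 eDiary days: SAP 9.3.

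**1. Reproduce the SAP's table.** When doses are not received, the week 4n interval should run from day 28(n − 1) + 1 to day 28n. All 13 rows match. For n = 12 this gives days 309 to 336; for n = 13 it gives days 337 to 364. The table is internally sound, and it includes month 13.

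**2. Start of the month-13 interval.** The week 48 target is 28 × 12 + 1 = day 337.

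- Clinic dose: 337 ± 4 = days 333 to 341.
- Home dose: days 334 to 342.
- Week 48 dose not received: day 337.

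**3. Month-13 days kept.** Days kept = max(0, cut-off − start + 1). The sentence does not tie week 48 to a day, so several readings are shown.

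| Cut-off | Start 333 | Start 337 | Start 341 | Start 342 (home) |
|---|---|---|---|---|
| Day 336 (end of week 48 interval) | 4 | 0 | 0 | 0 |
| Day 337 (week 48 target) | 5 | 1 | 0 | 0 |
| Day 341 (latest in-window visit) | 9 | 5 | 1 | 0 |
| Day 364 (week 52 row) | 32 | 28 | 24 | 23 |

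A cut at the subject's actual week 48 visit keeps 1 day, or 0 if the visit day is excluded or the dose is taken at home the next day.

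**4. Compare with the minimum.** Cutting at day 336, day 337 or the actual visit leaves 0 to 5 days. Cutting at day 341 leaves at most 9. All are below 14, so every month-13 value would be set to missing.

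**5. Check that month 13 is usable under the week 52 row.** The interval is 23 to 32 days long, and 28 if the week 48 dose is not received. The shortest scheduled diary period starts with a home dose on day 342 and ends before the earliest in-window week 52 visit, 365 − 4 = day 361. Diary days 342 to 360 number 360 − 342 + 1 = 19, so the 14-day minimum can still be met.

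**6. Share of the eDiary results.** The reported months are 1, 2, 3, 6, 10 and 13. One of six is affected, and it is the last.

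**The case against.** The strongest reply is that the section largely corrects itself. The sentence refers to a dosing schedule defined below it, that table has a week 52 row, the note asks for all available month-13 data, and SAP 6.6 works from the table. The only explicit exclusion in the paragraph concerns diary data after the end-of-study date, which would leave month 13 in for subjects who complete the study. On this view the phrase merely misdescribes when collection ends. This shows that the intent is clear and keeps the point minor. It does not remove the conflict, because nothing says that the table overrides the sentence.

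A second reply is that week 48 could mean the end of the SAP's week 48 visit window, day 351. That would keep 351 − 333 + 1 = 19 down to 351 − 342 + 1 = 10 days, so some subjects would reach 14. But SAP 6.4 assigns that window table to laboratory tests, vital signs, C-SSRS and office-visit PROs, and a cut at day 351 would still disagree with day 364.

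Two cautions stand:

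- In the available text of protocol Table 1, the daily clinical outcome rows show only three diary blocks and none clearly at weeks 48 to 52. The table may be broken by text extraction, so the synopsis and section 7.2.1.10 carry the point.
- Week 52 is itself a slightly loose label. The row ends at day 364, the target visit is day 365, and the note runs to the visit. With a visit on day 369, diary days 365 to 368 are in under the note and out under the row. That is a separate and smaller ambiguity.

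**Conclusion.** The concern holds. The week 48 cut-off in SAP 6.4 is wrong as written, and the rest of the SAP and the protocol's diary schedule keep the month-13 interval. Applied literally, it would leave 0 to 5 month-13 diary days (at most 9 on the day 341 reading) against a minimum of 14, and would remove month 13 for all four secondary endpoints. These counts assume visits within ±4 days of target and depend on how week 48 is read; the one reading under which some subjects reach 14 days uses a window table that the SAP does not apply to diary intervals.

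Severity is minor. The intended reading is clear, the diary data are collected in any case, and the efficacy analyses are descriptive with no formal tests. The primary adverse event endpoint and the office-visit questionnaires (MSQ, MIDAS) are unaffected.

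**What to change.** In the first sentence of SAP 6.4, change the limit of eDiary input, and the stated end of eDiary use, from week 48 to week 52. A reference in the same sentence to the end of the week 52 interval in the table would serve equally well and would give the limit a defined day. The cost is one phrase in the SAP. The interval table, the endpoint definitions and data collection need no change for this point.

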6.1 Definition of Terms Included in Study Endpoints

6.1.1 Safety Endpoints

Serious Adverse Event (SAE)

SAEs determined by the flag indicating if the adverse event is serious on the Adverse Events (AE) eCRF page will include those that occur after signing of the informed consent and up to and including end of study.

Treatment-Emergent Adverse Event

Adverse Events (AEs) recorded on the Adverse Events eCRF page that occur on or after first dose of investigational product as determined by the flag indicating if the adverse event started prior to the first dose on the Adverse Events eCRF and up to and including 112 days after the end of investigational product (16 weeks after the last dose of IP) or end of study, whichever comes earlier.

An AE that started in parent study 20120295 is only considered treatment emergent in the OLE study 20130255 if there is a worsening of the event. If the event is ongoing with no changes in severity, then it will not be considered an AE in 20130255.

Treatment-Related Adverse Event

A treatment-related AE is defined as a treatment-emergent adverse event that is considered by investigators to have reasonable possibility that it may have been caused by IP as determined by the flag indicating if the event is caused by investigational product on the Adverse Events eCRF page.

Columbia-Suicide Severity Rating Scale (C-SSRS)

The C-SSRS is a clinician rating of suicidal behavior and ideation. The version "Since Last Visit" will be used for this study. The C-SSRS consists of a maximum of 20 items to evaluate suicidal behavior and suicidal ideation. Please refer to [Appendix B](#) for more details.

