10.6.4 Columbia-Suicide Severity Rating Scale (C-SSRS)

No statistical testing will be performed on C-SSRS. The number and percentage of subjects reporting any suicidal ideation and any suicidal behavior will be summarized descriptively by treatment group and visit. **Shift table of C-SSRS maximum severity of suicidal ideation/behavior compared to baseline will be provided by treatment group.**

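### SAP 6.4 keeps one C-SSRS form per visit window, so a positive form from an unscheduled visit, and some early-termination forms, can be missing from the by-visit table

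*SAP*

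**What the plan says.** SAP 6.4 (Study Visit) maps each visit to a window of study days around a target day. Week 4 is days 2 to 43. Weeks 8 to 52 follow "28n-12 to 28n+15" with target 28n+1, for n = 2 to 13. When several visits fall in one window, the selection runs in this order:

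- A scheduled visit is taken however far it lies from target: "Unscheduled visit will only be used when there is no scheduled visit in the defined window". Unscheduled visits are identified by an event code ("including the unscheduled visits, ie, CPEVENT='UNSCHED").
- Among visits of the same type, the one nearest the target day is taken. For ties, "If two assessment dates are equidistant from the target date, the latter visit will be considered for analysis".

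The scope is explicit: "Above study visit table will be used for lab, vital signs, C-SSRS and PROs collected during office visit". Only the safety follow-up visit is exempt: "visit windows below only apply to visits other than safety follow-up visit".

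On the instrument, SAP 6.1.1 says: "The version 'Since Last Visit' will be used for this study". It sends the reader to Appendix B for details, and that appendix is redacted.

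SAP 10.6.4 plans two outputs. The first is a by-visit count: "The number and percentage of subjects reporting any suicidal ideation and any suicidal behavior will be summarized descriptively by treatment group and visit". The second is a shift table of maximum severity against baseline by treatment group, without a visit dimension. The set of records behind that maximum is not defined.

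Protocol 7.2.1.17 has the C-SSRS given at each study visit. In Protocol Table 1, ET shares the Week 52 / Month 13 column, and the C-SSRS is marked there.

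**The concern.** Keeping one record per window suits a measure of current state, such as blood pressure, where the retained value stands in for the discarded one. A form that asks what has happened since the last visit does not work that way. If a subject reports ideation at an unscheduled visit and the next scheduled form is negative, the two forms describe different periods and both are true. Keeping only the second records the subject as negative for that window.

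An ET form has a related problem. It covers the time after the last routine visit, so the routine form retained in the same window cannot contain what the ET form reports.

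The consequence is that a positive report of ideation or behavior can be absent from the one C-SSRS table whose record selection the SAP specifies.

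**Working it through.** **1. Windows.** Putting n into 28n-12 to 28n+15 gives:

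- n = 2: 44 to 71
- n = 3: 72 to 99
- n = 5: 128 to 155
- n = 13: 352 to 379

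All 12 formula windows match the SAP table. With Week 4 at days 2 to 43, the 13 windows are contiguous over days 2 to 379. They cover 42 + 12 × 28 = 378 days.

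**2. Unscheduled form, all scheduled visits attended.** Protocol 7.1 allows ±4 days around each visit. A visit on day 28n+1 ± 4 stays inside its own window, so every window contains a scheduled visit. Applying the rule to one extra unscheduled form on each possible day drops it on 378 of 378 days. The result is the same with scheduled visits all on target, all 4 days early or all 4 days late.

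Example: an unscheduled form on day 75 is positive and the Week 12 form on day 85 is negative. Both fall in 72 to 99, day 85 is used, and the table shows no report.

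**3. Unscheduled form, one scheduled visit missed.** With Week 24 missed, a form on days 156 to 183 (28 days) is kept as Week 24. The loss therefore depends on a scheduled visit having been attended in the same window.

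**4. ET form typed as scheduled.** The preference for scheduled visits does not apply here; the nearest-to-target rule does. Let the last routine visit be Week 4k (k = 1 to 12) and ET be j days later (j = 1 to 27). The window ends on day 28k+15.

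| Last routine visit | ET in same window | ET form dropped | Share of 27 days |
|---|---|---|---|
| On target, day 28k+1 | j = 1 to 14 | j = 1 to 14 | 14/27 = 52% |
| 4 days late, day 28k+5 | j = 1 to 10 | j = 1 to 10 | 10/27 = 37% |
| 4 days early, day 28k-3 | j = 1 to 18 | j = 9 to 18 | 10/27 = 37% |

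In the last row, for j = 1 to 8 the ET visit is nearer to target, or tied and later. It then replaces the routine form, which is the one lost.

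Example: the Week 20 visit is on day 141, 0 days from target, and ET is on day 150, 9 days from target. Both fall in 128 to 155, so the ET form is dropped. From day 156 it would fall in the Week 24 window and be kept.

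**5. ET form typed as unscheduled.** Every ET form sharing a window with the last routine visit would be dropped: 10/27 = 37% (late), 14/27 = 52% (on target) or 18/27 = 67% (early).

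The percentages in steps 4 and 5 treat each of the 27 days as equally likely. The documents give no distribution of ET timing. These are shares of possible days, not of subjects.

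**The case against.** Several points on the other side stand.

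- A reader might infer that the preference for scheduled visits removes ET forms as well. The documents do not support this. ET is a column of the visit schedule, and the SAP identifies unscheduled visits by event code without classing ET among them. An ET form is lost only through the nearest-to-target rule, and is otherwise kept.
- A reader might infer that suicidality is understated in the C-SSRS analysis as a whole. That is not shown. The maximum-severity shift table is not by visit and may already use every record. Its record set is undefined, which is an ambiguity and not a demonstrated loss.
- Appendix B is redacted and may contain a C-SSRS rule that overrides 6.4. It cannot be treated as silent.
- A reader might infer that positive reports are removed selectively, because unscheduled visits are prompted by concern. That is plausible, but the protocol describes no concern-triggered C-SSRS, and no document gives the number of such forms or the reason for them.
- The primary endpoint is AE incidence. SAP 6.4 gives adverse events study-phase windows, so suicidality recorded as an AE or SAE is untouched. The investigator's response to a positive report under Protocol 7.2.1.17 does not depend on this table either.

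These points limit the size of the problem but do not remove it. The rule is written out and names the C-SSRS, and the by-visit count follows from it. Elsewhere the SAP says so when it wants results from any time: 10.6.2 bases its main laboratory shift tables on the worst post-baseline grade, and 10.6.6 lists every subject who was ever antibody-positive. Section 10.6.4 has no comparable statement for the C-SSRS.

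**Conclusion.** The point holds for the by-visit ideation and behavior table. As written, SAP 6.4 always drops an unscheduled C-SSRS form for a subject who attends every scheduled visit. It drops an ET form typed as scheduled when another scheduled visit in the same window is closer to target. A positive report can therefore be missing from that table.

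This rests on two assumptions. The first is that sites anchor the recall period to the most recent visit, including unscheduled ones, as the version name implies. The second is that the redacted Appendix B does not already set a different rule.

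The number of forms affected cannot be estimated from the documents, and neither the direction nor the size of any effect on the overall suicidality picture is established. The table is descriptive, with no statistical testing. This is a should-fix point: the remedy is cheap and the outcome is a safety one, but it does not threaten the primary endpoint.

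**What to change.** - In SAP 6.4, exempt the C-SSRS from single-record selection. For each window, use the most severe ideation and the most severe behavior over all assessments in it, whether scheduled, unscheduled or ET.
- In SAP 6.4, state whether ET visits count as scheduled or unscheduled for windowing. The other data under the rule need this too.
- In SAP 10.6.4, state that the maximum-severity shift table uses every assessment after Day 1, including unscheduled, ET and safety follow-up. An any-time post-baseline incidence of ideation and of behavior would be a useful optional addition; it is not currently planned.
- If Appendix B already sets such a rule, have 6.4 refer to it and take the C-SSRS off the list of data governed by the window table.

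The cost is a few sentences in the SAP and a change to one derivation. No new data are needed.
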